11 DATA QUALITY ASSURANCE

Acutus Medical will oversee the data collection for this study in accordance with Good Clinical Practices (GCP), regulatory requirements, the Data Management Plan (DMP), and corporate QAPs. Data will be collected and stored in an Electronic Data Capture (EDC) system. Data will be reviewed for accuracy and completeness by Acutus Medical (or designees). Any discrepancies will be resolved with the Investigator or designees, as appropriate. In order to preserve data integrity and security of the data, access to the study in the EDC will be controlled by Acutus Medical and shall be limited to appropriately trained personnel with assigned log-on credentials.

11.1 Site Data Management

For the duration of the study, the Investigator and their designees will maintain complete and accurate documentation, including but not limited to medical records, study progress notes, laboratory reports, signed patient ICFs, correspondence with the reviewing EC, correspondence with Acutus Medical (or designees) and study monitors, AE reports, and information regarding subject discontinuation/withdrawal or completion of the study.

The Investigator/Institution will permit direct access to source data and documents in order to complete study-related monitoring, audits, EC reviews, event adjudication, and regulatory inspections that may be performed. The Investigator will obtain, as part of the ICF process, permission for authorized Sponsor employees, study monitors or regulatory authorities to review, in confidence, any records that identify subjects in this study.

11.2 Subject Identification

Subjects will be identified on all eCRFs and source documents by a unique, anonymized identification reference number, which will be issued once the ICF has been signed. An identification reference number may not be reused for any reason.

11.3 Screen Failure Subjects

Subjects who are screened for the study but are not enrolled for any reason will not be followed and their data will not be used for any outcomes analysis.

11.4 Subject Study Completion and Withdrawal

A subject will be considered completed when the 12-month visit is completed, and all data collection is complete. Subjects who withdraw for any reason will have all available data entered into the database. Reasons for withdrawal will be entered on the Study Exit eCRF.

11.5 Subjects Lost-to-Follow-Up

A subject will be considered LFU from the last missed clinical evaluation if all reasonable efforts made to contact the subject and request their continued participation in the study have failed. All attempts to contact the subject will be documented.

11.6 Confidentiality of Data

Information regarding study subjects will be kept confidential and managed according to the requirements and regulations of the local and national governing bodies and QAPs of Acutus Medical or participating Clinical Research Organizations (CROs).

All data and information collected during this study will be considered confidential by Acutus Medical and their delegates. All data used in the analysis and summary of this study will be anonymous and without reference to specific subject names. Access to subject files will be limited to authorized personnel of Acutus Medical (including core labs), the Investigator, Clinical Site research staff, and authorized Regulatory Authorities. Authorized regulatory personnel have the right to inspect and copy all records pertinent to this study.

11.7 Source Documents

Source data encompasses all information, original records of clinical findings, observations, or other activities, which are required in a clinical trial for the reconstruction and evaluation of the trial. Examples of these original documents, and data records include, but are not limited to, hospital records, clinical and office charts, laboratory notes, memoranda, subject diaries or evaluation checklists, recorded data

from automated instruments, copies or transcriptions certified after verification as being accurate and complete, copies of clinic and procedural site coding and billing records, microfiches, photographic negatives, microfilm or magnetic media, X-rays, patient files, and records kept at the pharmacy, and at the laboratories involved in the clinical trial.

Regulations require that the Investigator maintain information in the patient's medical records that corroborate data collected for the study. In order to comply with these regulatory requirements, the following is a list of information that should be maintained, at a minimum:

- Medical history/general physical condition of the subject before involvement in the study, which will be of a sufficient nature to verify the protocol eligibility criteria.
- Study/progress notes, including the date of entry into the study, documenting the following:
 - The general health of the subject.
 - The discussion of the study risks and benefits with the patient.
 - Completion of the ICF process.
 - A statement that the subject reviewed and signed the patient informed consent form.
- Dated notes from each subject visit to support all data recorded on the eCRFs.
- AEs reported and their continuation or resolution at each visit, including supporting documentation, such as discharge summaries, lab results, non-invasive testing reports, etc.
- Notes regarding AADs taken during the study (including start and stop dates, dosage, and routes of administration, if known).
- Subjects general health and medical condition upon completion of, or withdrawal from, the study.

11.8 Electronic Case Report Forms

This study will use an electronic Case Report Form (eCRF) as the primary data collection instrument and will record data by electronic capture. All data requested on the eCRF must be entered within two (2) weeks of the data being generated/collected. All missing data must be explained. If a data entry error has been made, the corrected

information will be entered on the eCRF. All such changes are recorded in the audit and queries reports.

Specific instructions to complete the eCRFs will be provided to the Investigator and other site personnel, as appropriate. The Investigators (and designees) are responsible for reporting clinical study-requested information on the eCRFs.

11.9 Records Retention

The Investigator will retain study essential documents for two (2) years after formal closure or discontinuation of the trial. These documents must be retained for a longer period if required by an agreement with Acutus Medical or defined by local or national regulations. Acutus Medical will inform the Investigator/Institution as to the date of formal closure or discontinuation of the trial.

11.10 Clinical Monitor

A CRO may be designated as the clinical monitor for this study. Their personnel will be qualified by training and experience to oversee the conduct of the study. The Clinical Monitors (also known as Clinical Research Associates (CRAs)) responsibilities include maintaining regular contact with each investigational site through telephone contact or email to ensure that: 1) the CIP/protocol is followed; 2) complete, timely, and accurate data are submitted; 3) problems with inconsistent and incomplete data are addressed; 4) complications and UADEs are reported to the Sponsor; and 5) the site facilities continue to be adequate.

11.11 Clinical Data Monitoring Procedures

Monitoring requirements will be defined in the Clinical Monitoring Plan (CMP). The Clinical Monitors (or designees) may conduct site visits at the study facilities to monitor the study, which will be in compliance with the CIP/protocol, QAPs, and the CMP. When a site visit is performed, the Investigational site agrees to allow the monitors and other authorized Acutus Medical personnel access to information. The monitors may verify data entered into the eCRFs against hospital/clinic records or other source documents in order to ensure accuracy and completeness of the eCRFs for each subject. Clinical Investigators and their staff agree to assist the monitors in their activities. Requests may be made to review patient charts by Acutus Medical personnel and/or designee(s) so that protocol adherence and source documentation can be verified.

Monitoring activities may include, but are not limited to:

- Evaluation of subject screening and selection methods

- Verification of signed informed consent for each subject
- Verification of source documentation against completed case report forms for each subject
- Assurance that required study reports, including reports to the applicable EC, are generated in a timely manner
- Monitoring of Safety Events, including device deficiencies that may have led to an SAE
- Monitoring of device deficiencies, irrespective of associated safety events
- Review of protocol deviations
- Overall study compliance
- Review of the Investigator Site File (ISF)

11.12 Investigator Responsibilities

The investigator is responsible for ensuring that the clinical study is performed in accordance with the protocol, the Declaration of Helsinki, the principles of GCP, International Organization for Standardization (ISO) 14155:2011, applicable regulatory requirements, and institutional procedures.

11.13 Deviations from the Clinical Investigational Plan

A CIP/protocol deviation is defined as an event in which the Investigator or site personnel deviates from the study protocol or study procedures. It is the Investigator's responsibility to ensure that there are no deviations from the protocol. On a rare occasion, a waiver to a screening test, exclusion criteria, or protocol-specific procedure may be granted in advance by Acutus Medical and must be reported in full compliance with all established procedures and conditions of the reviewing EC.

An Investigator may deviate from the protocol without prior written approval from Acutus Medical in cases of medical emergencies to protect the life or physical well-being of a subject. In the event of an emergent deviation, the Investigator is required to notify Acutus Medical and the applicable EC as soon as possible, but no later than five (5) business days from the occurrence of the deviation from the protocol.

Except in such an emergency, prior approval by Acutus Medical is required for changes in, or deviations from, the protocol. Additionally, if these changes or deviations affect the scientific soundness of the investigational plan or the rights, safety, or welfare of human subjects, EC notification is required.

Prior approval is generally not expected in situations where unforeseen circumstances are beyond the Investigator's control (e.g., the subject was not available for a scheduled follow-up office visit or has moved without providing a forwarding address). These events, although outside the Investigator's control, are still required to be reported on the appropriate Protocol Deviation eCRF in order to ensure that all deviations from the standard subject population are adequately documented and reported. The Investigator will inform Acutus Medical and the reviewing EC of all protocol deviations as per the EC requirements established for this study.

If Acutus Medical becomes aware that an Investigator is not complying with any part of the CIP, including the signed Investigator Agreement (IA), the protocol, or any conditions of approval imposed by the reviewing EC, Acutus Medical will immediately secure compliance, and may suspend the Investigator's participation (including enrollment at the site). Acutus Medical may terminate an Investigator's participation in the study at its discretion.

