OUTCOME MEASURES	
The measurable objectives are a descriptive analysis of the following:
 
 • At the procedure conclusion, confirmation of electrical isolation of all pulmonary veins and elimination/modification of all non-PV targets as identified by the AcQMap System • Recording of all subjects who are atrial fibrillation free from events lasting > 30 seconds at 6-, and 12-months as measured by a 48-hour continuous ECG 
 ○ A subset analysis of AAD use ○ A subset analysis of subjects with freedom from AF/AT/AFL events lasting > 30 seconds as measured by a 48-hour continuous ECG • Documentation of procedure data including total time, fluoroscopy time, ablation times for PVI, and ablation times for non-PV targets • Safety – Recording of all device and procedure related safety events through 24 hours post-ablation
INCLUSION CRITERIA	
The patient population will consist of men and women eighteen (18) years of age or older, scheduled for a repeat endocardial ablation of AF following a failed ablation for atrial fibrillation.
 
A potential subject will be eligible for study enrollment only if all the following inclusion and none of the exclusion criteria apply:
 
IC 1 Male or female eighteen (18) years of age or older IC 2 Currently scheduled for a repeat endocardial ablation of AF IC 3 Willingness, ability, and commitment to participate in baseline and follow-up evaluations for the full length of the study IC 4 Willingness and ability to give informed consent

EXCLUSION CRITERIA	
EC 1 In the opinion of the Investigator, any known contraindication to a left-atrial ablation or concerns for left-atrial thrombus EC 2 No more than two (2) previous left-atrial ablations EC 3 Atrial arrhythmias secondary to electrolyte imbalance, thyroid disease, or any other reversible or non-cardiac cause EC 4 Structural heart disease or implanted devices as described below:
 
 a. An implanted pacemaker or ICD b. Previous cardiac surgery, ventriculotomy, or atriotomy (excluding atriotomy for CABG) c. Previous cardiac valvular surgical or percutaneous procedure, or prosthetic valve d. Interatrial baffle, closure device, patch, or PFO occluder e. Presence of a left atrial appendage occlusion device f. Unstable angina or ongoing myocardial ischemia

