6.4 Clinical Study Sample Size and Clinical Sites

Up to one hundred (100) patients will be treated at up to fifteen (15) clinical sites in Europe. The sample size will include only those that complete an ablation procedure using the AcQMap technology (Treatment Subjects).

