6.5 Clinical Study Enrollment Definitions

For the purposes of this clinical study, the following definitions regarding the status of a subject will apply:

Pre-Treatment Subject – Any subject who has signed an informed consent form, is deemed study eligible by meeting all of the inclusion and none of the exclusion criteria, and who has the venous access portion of the ablation procedure initiated. Pre-Treatment subjects that do not complete the AcQMap procedure will be followed for adverse events through hospital discharge. In addition to the discharge eCRF, a study completion eCRF will be completed. No follow-up beyond the hospital discharge will be required.

Treatment Subject – Any pre-treatment subject who completes the ablation procedure using the AcQMap System. A completed ablation procedure is defined as a procedure where the PVI was evaluated and additional non-PV targets were mapped and ablated using the AcQMap System. Treatment subjects should be followed for all study outcome measures for the full duration of the clinical study.

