6.6 Clinical Study Population

The patient population will consist of men and women eighteen (18) years of age or older, scheduled for a repeat endocardial ablation of AF following a failed ablation for atrial fibrillation.

A potential study subject will be eligible for study enrollment only if all the following inclusion and none of the exclusion criteria apply:

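### Section 11.13 lets the sponsor waive exclusion criteria in advance, which does not fit the unqualified eligibility rule and leaves a waived patient with no defined status, follow-up or place in the analysis

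*Combined protocol and SAP*

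**What the plan says.** **Eligibility.** Section 6.6 is unqualified: "A potential study subject will be eligible for study enrollment only if all the following inclusion and none of the exclusion criteria apply". The synopsis states the same rule: "A potential subject will be eligible for study enrollment only if all the following inclusion and none of the exclusion criteria apply".

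**Subject status.** Section 6.5 requires that a Pre-Treatment Subject "is deemed study eligible by meeting all of the inclusion and none of the exclusion criteria". A Treatment Subject is then defined as "Any pre-treatment subject who completes the ablation procedure using the AcQMap System". The second category therefore sits inside the first. Section 6.4 counts only Treatment Subjects toward the sample of up to 100.

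**Follow-up.** Section 6.5 ties follow-up to these categories. Pre-Treatment Subjects who do not complete the procedure are followed for adverse events to discharge. Treatment Subjects are followed for all outcomes over the full study.

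**Waivers.** Section 11.13 says: "On a rare occasion, a waiver to a screening test, exclusion criteria, or protocol-specific procedure may be granted in advance by Acutus Medical". The sentence goes on to say that a waiver "must be reported in full compliance with all established procedures and conditions of the reviewing EC". The same section requires the ethics committee to be notified when a deviation affects the validity of the plan or the protection of subjects. Section 11.13.2 says that documented prior approval by the committee may be needed for such a deviation.

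**Analysis.** Section 8 plans descriptive statistics only, with no hypotheses and no power calculation. It names no analysis set. Section 5.2 foresees a comparison of 6- and 12-month success with historical controls from the literature.

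**The concern.** Sites and analysts cannot apply all of these sections as written. The eligibility rule and the subject definitions allow no exception, while Section 11.13 creates one and does not say what becomes of the patient.

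Two things are at stake. The first is subject protection. The waiver wording covers the exclusion criteria in general, so nothing exempts those that serve safety: EC 1 (contraindication to left-atrial ablation or concern for thrombus), EC 5 (clotting or bleeding disease) and EC 6 (pregnancy or lactation). Screening tests can be waived as well, so the check on a criterion can be lifted along with the criterion.

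The second is a clear population. With one arm and no randomization, the descriptive results and any comparison with the literature are read against the stated eligibility criteria. The sponsor grants the waivers. It also attends every procedure (Section 9.4), evaluates related adverse events (Section 9.5) and may use the data in a regulatory filing (Section 13.2). A rule fixed in advance is worth more in that setting than case-by-case discretion.

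**Working it through.** The plan gives no figure to reproduce, so the check is mainly textual.

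**Step 1: follow a waived patient through the definitions.**

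1. The patient meets an exclusion criterion, and the sponsor waives it under Section 11.13.
2. Under Section 6.6 and the synopsis the patient is not eligible, because an exclusion criterion applies.
3. Under Section 6.5 the patient is not a Pre-Treatment Subject, because that status requires that no exclusion criterion is met.
4. The patient is therefore not a Treatment Subject, because that category is drawn from Pre-Treatment Subjects.
5. Under Section 6.4 the patient is not in the sample, because only Treatment Subjects count.
6. The two follow-up rules in Section 6.5 attach to the two categories, so neither applies.
7. Section 8 does not say whether or where the patient's data appear.

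**Step 2: compare the oversight provisions.**

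| Situation | Ethics committee role |
|---|---|
| Waiver (11.13) | reporting under the committee's procedures and conditions |
| Deviation affecting validity or subject protection (11.13) | notification |
| The same kind of deviation (11.13.2) | prior approval may be needed |
| Amendment changing subject care or safety (11.15.1) | documented approval before use |

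An amendment touching safety needs approval first. A waiver of a safety exclusion for one patient carries no equally explicit requirement.

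**Step 3: bound the numerical effect, as illustration only.** Inputs: N = 100 (the maximum in Section 6.4), k waived patients, and AF-free proportion p among eligible patients. Both k and p are assumptions. The step also supposes that waived patients are counted within the 100, which no section states.

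Observed proportion = ((100 - k) × p + s) / 100, where s is the number of successes among the waived, from 0 to k. In percentage points, the shift from p therefore runs from -k × p to +k × (1 - p).

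Example with k = 5 and p = 0.70: 95 × 0.70 = 66.5, so the observed figure lies between 66.5% (all waived fail) and 71.5% (all succeed), a shift of -3.5 to +1.5 points.

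| p | Shift, k = 1 | Shift, k = 5 | Shift, k = 10 | Exact 95% interval, n = 100 |
|---|---|---|---|---|
| 0.50 | -0.5 to +0.5 | -2.5 to +2.5 | -5.0 to +5.0 | 39.8% to 60.2% |
| 0.70 | -0.7 to +0.3 | -3.5 to +1.5 | -7.0 to +3.0 | 60.0% to 78.8% |
| 0.80 | -0.8 to +0.2 | -4.0 to +1.0 | -8.0 to +2.0 | 70.8% to 87.3% |

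Even at k = 10 the extreme shifts stay inside the interval. At p = 0.80, for instance, the downward shift is 8.0 points and the lower limit lies 80.0 - 70.8 = 9.2 points below.

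**The case against.** The best reply is that this is a rule and its exception: a deviations section always departs from some rule. The exception is also limited. Waivers are meant to be rare, are granted beforehand and are reported under ethics committee conditions. Section 11.13 adds notification duties, Section 11.13.1 requires dates and reasons for each deviation, and Section 11.11 lists review of deviations among possible monitoring activities. The 24-hour adverse event duty in Section 9.1 is not worded by subject category, so early events would probably be reported anyway. One sentence on how waived patients are classified would close the gap without ending waivers.

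Much of this stands. The safeguards are real, and the reporting duty is part of the waiver sentence itself. But no number gives meaning to rare, no criterion is off limits, and an exception that leaves its own patients without a status is incomplete.

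A reader might infer three stronger points that the documents do not support:

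- **That waived patients would be counted among the 100.** No section says so. Sections 6.4 and 6.5, read literally, leave them out.
- **That the sponsor chooses who enters.** The clause allows the sponsor to admit an otherwise ineligible patient. Investigators still screen patients, and EC 1 and EC 8 rest on the investigator's judgement.
- **That the AF-free proportion would be materially biased.** The bounds above depend on assumed counts and extreme outcomes and stay within sampling error. The study is descriptive, and the literature comparison is not among the measurable objectives in Section 6.2.1.

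**Conclusion.** The point holds as a matter of internal consistency and subject protection. Section 11.13 cannot be applied together with the synopsis and Sections 6.5 and 6.6 as written. Nothing in it keeps a safety exclusion from being waived, and prior ethics committee approval is not expressly required. A waived patient has no defined follow-up, place in the sample or place in the analysis.

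The effect on the results is likely to be small. If a waived patient were counted, each would move the AF-free proportion by less than one point for p between 0.50 and 0.80. If not counted, the reported proportion would not change, but the plan would not say where that patient's outcome is shown. The textual conclusion needs no numerical assumption. It rests only on a literal reading of the definitions. This is a cheap improvement, not a threat to the study's main results.

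**What to change.** 1. In Section 11.13, delete exclusion criteria from the waiver sentence, together with waivers of the screening tests that verify them. Leave the emergency deviation clause as it is.
2. Reconcile the synopsis and Sections 6.4 to 6.6, 11.13 and 11.13.2, so that eligibility, subject status and the ethics committee's role read the same way throughout.
3. In Sections 6.5 and 8, state what happens if an ineligible patient is nonetheless treated: follow the patient in full, keep the patient in all safety tabulations, list the case as a protocol deviation, and show the 6- and 12-month AF-free proportions with and without such patients.

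If the sponsor prefers to keep waivers, the text must at least say who decides, what the ethics committee does beforehand, and how waived patients are classified, followed, counted and reported. This is the weaker option, because the safety exclusions would stay open to waiver.

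A related correction is needed for EC 2. It lists having no more than two previous left-atrial ablations as an exclusion, whereas Section 6.2 describes that group as the study population. The wording should be reconciled in the text and not handled by waiver.

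**Cost:** a few words, a short paragraph and one additional table. The downside is that a few borderline patients could not be enrolled.
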